Azathioprine is first converted to 6-mercaptopurine in the liver. In red blood cells, hypoxanthine guanine phosphoribosyltransferase (HPRT) converts 6-mercaptopurine to 6-thioninosine-5' monophosphate, which is then converted to either 6-thioguanine nucleotides (6-TG) or 6-methyl-mercaptopurine ribonucleotides (6-MMP). 6-TG is the metabolite that is associated with immunosuppression, and thus may help decrease disease activity and lead to or maintain remission in IBD (Belaiche et. al, 2001, p. 72). It has a long half-life in red blood cells and other tissues. Thus, prolonged treatment is needed for it to accumulate to steady-state levels (p. 72). 6-TG is also cytotoxic and associated with suppression of bone marrow at levels greater than 400 pmol/8x10⁸ RBC (MacDermott, 2016). However, levels between 230 and 400 pmol/8x10⁸ RBC seem to be optimal for treating IBD and achieving remission. The other end metabolite of azathioprine/6-mercaptopurine, 6-MMP, is associated with hepatotoxicity at levels greater than 5700 pmol/8x10⁸ RBC (MacDermott, 2016). If thiopurine methyltransferase (TPMT) is deficient, bone marrow toxicity can occur due to elevated levels of 6-TG nucleotides. Thus, it is important to monitor the metabolism of azathioprine and 6-mercaptopurine through the levels of 6-TG and 6-MMP.

Methods

Research design: The study will be a prospective study in a cross over design, with each patient acting as a control for him/herself. Subjects will be patients contacted from a Rush University Medical Center database that are currently prescribed azathioprine and/or 6-mercaptopurine. They will be asked to take their medication at a determined time each day (morning or evening), complete questionnaires, and come in to get labs drawn. Data obtained will be analyzed according to statistical methods listed below in order to determine significance of association.

Power and Sample Size: There have been no prior studies testing the role of chronotherapy and IBD, therefore no knowledge exists on the anticipated effect. We aim for a prospective study to offer enrollment to all subjects who meet the study qualifications. For a mean difference of 5% and standard deviation of 20, we calculated that we will need to enroll 128 subjects to provide a power of 80% for a significance level of $\alpha=0.05$.

Inclusion Criteria: Patients with IBD who have taken, or are currently taking, azathioprine or 6-mercaptopurine.

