All power estimates were computed using R package pwr, and we assume a Type I error rate of 0.05 and a 2-sided test for all analyses. Power estimates were derived from the data from prior unpublished studies. The primary endpoint of this study will be metabolites of 6-mercaptopurine. For Aim 1, previous studies have found that circadian enzymes can alter metabolites about 12% by different circadian controlled genes. With 128 UC subjects and effect size of 0.1 this will give us a 98% power to detect a difference in serum metabolites with a paired Wilcox Signed Rank test at alpha=0.05 level, and 84% power if gender is used as an independent variable. These conservative estimates provide a good estimate of the power to detect differences in metabolites chronotherapy in IBD patients. We anticipate we will have nonparametric data and will use the Wilcoxon match-pair test for analysis for inflammatory cytokines. This will be a nonrandomized trial that will not control for order effects, but other factors that are recorded such as cigarette smoking will be used as a covariate in multivariate analysis with analysis of variance (ANOVA) and linear regression as indicated. For Aim 2, a validated chronotype questionnaire (Munich Chronotype Questionnaire) will be compared optimal 6-mercaptopurine. Corrected midpoint of sleep will then be compared to 6-MP metabolites to see if chronotype impacts metabolite profiles. Data will be presented as median \pm range for variables that can be considered nonparametric. All analyses will use R (v.3.2.5) and SPSS (SPSS Inc., Chicago, IL).

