Our study is based on the potential circadian oscillation of the enzymes responsible for metabolizing IMs (as above), as well as that of the pro- and anti-inflammatory cytokines also described above. The oscillatory nature of these enzymes and cytokines may differ amongst individuals based on their circadian makeup, which we hope to assess via the chronotype surveys (Owl and Lark, MCTQ, RU SATED). We will assess the potential benefit of taking IMs in the morning vs evening by assessing changes in clinical outcomes, laboratory data, endoscopic findings/imaging (if subjects undergo a colonoscopy or imaging as part of their standard care while a part of this study), and quality of life surveys (Harvey Bradshaw, IBDQ). The study is a prospective cross-over study in which each patient is assigned to the morning or evening group based on when they currently take their medication. Therefore, each subject serves as his/her own control.

Study Outcomes: The goal of this study is to determine whether time of delivery of medication affects the efficacy or side effects of this medication. The study outcomes include 1) IBD clinical status as either a) remission defined per no need for step-up therapy (steroid, initiation of anti TNF, change of TNF, or surgery), or b) complications (fistula or abscess) 2) changes in the IBDQ and Harvey Bradshaw questionnaires.

Expected Outcomes: The expected outcome of this study is that there will be a difference seen in disease outcomes for IBD between the different groups based on what time they are taking their medication. Based on the known enzymatic pathways of IM metabolism and their potential circadian rhythm, we expect to see variation in the efficacy as well as toxicity of IMs when administered at different times of the day. Understanding these variations and determining the predicting factors (e.g., chronotypes) can lead to circadian-based administration of IMs to increase the efficacy of the drug while minimizing its side effects. We expect to see differences in the IBD quality of life questionnaire and the Harvey Bradshaw questionnaire from before the intervention to after the intervention, as well as differences in clinical disease activity as determined by levels of metabolites, endoscopic findings, and imaging, between the two groups.

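### Expected Outcomes looks for differences in levels between two groups defined by patients' own dosing habit; that comparison is confounded and is not the within-patient contrast for which the study was sized

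*Combined protocol and SAP*

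**What the plan says.** All references are to the combined protocol and SAP.

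- **Methods, Research design** describes a crossover "with each patient acting as a control for him/herself".
- **Power and Sample Size** states "For a mean difference of 5% and standard deviation of 20, we calculated that we will need to enroll 128 subjects", for 80% power at a significance level of 0.05.
- **Study and Data Analysis** makes 6-mercaptopurine metabolites the primary endpoint and names a paired signed-rank test for them. It adds that the trial is not randomised and that order effects are not controlled. In the same section, "each patient is assigned to the morning or evening group based on when they currently take their medication", and morning versus evening is to be judged through changes.
- **Description of Procedures** gives the direction: morning takers move to evening and evening takers to morning, for 10 weeks. Blood is drawn before the switch and at week 10. Endoscopy is collected only if it happens to be done, and no pre-switch endoscopy is scheduled.
- **Expected Outcomes** first anticipates a difference in disease outcomes between groups. It then treats the questionnaires as before/after comparisons, and separately expects "differences in clinical disease activity as determined by levels of metabolites, endoscopic findings, and imaging, between the two groups".

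**The concern.** Design, sample size and named metabolite test are all within-patient. Expected Outcomes words the metabolite, endoscopy and imaging result as a contrast between groups, and its mention of levels, set against before/after questionnaires, reads most naturally as a comparison of week-10 values.

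That comparison asks a different question. Patients placed themselves in the groups through their earlier habit, so anything tied to habit (which drug, tolerability, work pattern, chronotype) is part of the group difference. The protocol itself suggests that circadian makeup may alter enzyme and cytokine rhythms, so chronotype could plausibly bear on both habit and metabolites.

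Three things are at stake:

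- A difference in week-10 levels could arise with no timing effect.
- A null result could simply reflect low power.
- With two contrasts available for one question, and only one of them tied to a test, the more favourable could be reported.

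**Working it through.** **Inputs.** Mean difference 5, SD 20, N = 128 and power 80% (Power and Sample Size); two-sided alpha 0.05 (Study and Data Analysis). The plan does not say whether 20 is the SD of within-patient differences or of levels. It gives no habit split and no within-patient correlation (rho). Those are assumptions below, shown as ranges. Power is by t-test, as an approximation to the planned rank test.

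**1. The plan's own figure.** Paired t-test, d = 5/20 = 0.25: n = 127.5, so 128, with 80.2% power. The alternatives do not give 128: a one-sided paired test needs 101, and two independent groups need 253 each. So 20 acts as the SD of the within-patient difference.

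**2. What each contrast estimates.** Let T be the morning-minus-evening effect, P a period effect common to all patients, and H the difference between habitual evening and habitual morning takers at the same dosing time. Assume T is the same in both groups.

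- Week-10 levels, morning group minus evening group: T + H. H cannot be separated from T. A hypothetical H of 5 would equal the whole target effect.
- Change in evening-to-morning switchers: P + T. Change in morning-to-evening switchers: P − T. Their difference is 2T, so stable H and common P both drop out.
- Pooled morning minus evening within patients: T + P × (evening takers − morning takers)/128. H drops out. P drops out only with an even split; at 102:26 a share of (102 − 26)/128 = 59% of P remains in absolute size.

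**3. Power for week-10 levels.** At 64 per group and level SD 20, the standard error is 20 × √(2/64) = 3.54 and 5/3.54 = 1.41. Power is 28.9% (29.3% by normal approximation). If 20 is the SD of differences, the level SD is 20/√(2(1 − rho)):

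| rho | Level SD | Power, 64/64 |
|---|---|---|
| 0 | 14.1 | 51% |
| 0.3 | 16.9 | 38% |
| 0.5 | 20.0 | 29% |
| 0.7 | 25.8 | 19% |
| 0.8 | 31.6 | 14% |
| 0.9 | 44.7 | 10% |

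**4. Power for changes between switch directions.** The expected difference is 2 × 5 = 10, and the SD of change is 20. At 64/64 the standard error is again 3.54 and 10/3.54 = 2.83, the same ratio as the paired test, 5/(20/√128) = 2.83. Power is 80.1%.

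**5. Uneven habits.**

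| Split | Week-10 levels (difference 5, SD 20) | Changes (difference 10, SD 20) |
|---|---|---|
| 64/64 | 29% | 80% |
| 96/32 | 23% | 68% |
| 102/26 | 20% | 62% |
| 115/13 | 14% | 40% |

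**The case against.** The strongest reply is that no test of week-10 levels is planned. The sentence is an expectation, the metabolite test is paired, and Study and Data Analysis speaks of changes with each patient as own control. This stands: a reader might infer that the plan commits itself to an unpaired group comparison as its analysis, and the documents do not support that. What remains is that the plan states its expected result on a scale its named test does not address, and never says whether levels or changes are meant.

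A reader might also infer that any comparison between these groups gives up the self-control. It does not. The groups switch in opposite directions and both blood draws are planned for everyone, so comparing changes keeps each patient as own control.

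Nor is 29% a figure from the documents. It needs an even split and a level SD of 20, which together with an SD of differences of 20 implies rho = 0.5. The 80% is the general figure in Power and Sample Size, which names no endpoint; for metabolites, Study and Data Analysis claims 98% at an effect size of 0.1. That claim is a separate matter.

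Finally, drug and chronotype are recorded, and covariate-adjusted ANOVA and regression are foreseen. This helps in part, but adjustment reaches only recorded factors, and the plan does not tie it to this group contrast. The documents contain no data showing that habit is related to metabolites, so confounding is a structural risk of unknown size.

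**Conclusion.** The concern holds for a comparison of post-switch levels between the habit-based groups. Such a comparison is confounded by habit, differs from the paired contrast behind the 128, and comes with no test, split, between-patient SD or power. For a difference of 5 at 64 per group, power is about 29% with a level SD of 20, or about 10% to 51% if 20 is the SD of differences and rho runs from 0.9 to 0. Nothing in that range comes near 80%, and uneven habits lower it further.

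It does not follow that the study has 29% power. The paired calculation reproduces, and the comparison of changes has about 80% power at an even split, provided the timing effect is the same in both switch directions and the SD of change is 20. The defect lies in how the contrast is specified. It should be corrected before analysis, because it decides which result may be read as an effect of timing.

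**What to change.** In Expected Outcomes, replace both between-group statements with text to this effect:

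1. For metabolites and other outcomes measured at both visits, the timing effect is estimated within patients as morning minus evening dosing. The sign must be stated, because an after-minus-before difference pooled over opposite switches would tend to cancel a timing effect.
2. Any between-group comparison is of within-patient changes (week 10 minus baseline) between the two switch directions. This keeps the self-control and removes a period effect common to both groups. The groups remain non-randomised, and the observed split should be reported because power falls as it becomes uneven.
3. Week-10 levels, and endoscopy or imaging without a pre-switch value, are shown by group descriptively, with no conclusion about timing.

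Study and Data Analysis should use the same definition of the contrast. The change is to wording only, with no added visits or patients. The cost is that the unpaired endoscopy and imaging comparison can no longer support a timing conclusion. The text should not claim paired endoscopy or imaging, because the protocol does not schedule the pre-switch examination.
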